7.4.4. Shift in Laboratory toxicity grade post-baseline

- Toxicity grade shifts from baseline of ≥ 2 grades for each analyte will be summarized for each year interval and at any time post-baseline. The display will summarize the number (%) of subjects with at least one ≥ 2 grade shift as well as the specific shift categories: Grade 0 to 2, Grade 0 to 3, Grade 0 to 4, Grade 1 to 3, Grade 1 to 4, and Grade 2 to 4.
- See Appendix 2: Assessment Windows for handling of the post-last dose 16 Week follow-up visit.

7.4.5. Laboratory Reference Range Shifts

- Summaries will be presented by parent randomized treatment group, and total Safety population.
- Laboratory reference range shifts will be summarized only for laboratory tests without toxicity grades.
- A laboratory value that is outside of normal range will be considered abnormal (above or below).
- Shifts relative to the normal range will be summarized for each analyte, at each belimumab visit, as follows:
 - o 'n' represents the number (%) of subjects with a low, high or normal value at the specified visit.
 - o For subjects with a low value at the specified visit, the shift categories relative to baseline are shown as either remained low, or normal/high to low.
 - o For subjects with a high value at the specified visit, the shift categories relative to baseline are shown as either remained high, or normal/low to high.

 For subjects with a normal value at the specified visit, the shift categories relative to baseline are shown as either remained normal, or high to normal, or low to normal.

7.4.6. Immunogenicity

- Serum samples for anti-belimumab anti-body measurements were obtained from subjects per the protocol.
 - o Immunogenicity testing in BEL114333 subjects used a tiered approach. The binding assay (to detect the presence of anti-drug antibodies) consisted of 3-testing steps: screening, confirmation and titer. At each scheduled visit, the screening assessment was performed resulting in a positive (above screening cut point) or negative (below screening cut point) result. Samples testing potentially positive in the screening assay were then tested in the confirmation assay. Samples then testing positive in the confirmation assay (above confirmation cut point) were considered confirmed and reported as positive; samples with a result below the confirmation cut point were reported as negative for the binding assay. Samples with a confirmed positive result were also run in the titration assay, and a titer value reported. In addition, samples testing positive for the binding assay were also tested in the neutralization assay (to determine if ADA were neutralizing), which also produced a result of positive or negative.
 - o Binding confirmatory assay results will be categorized for analysis as
 - negative,
 - persistent positive (defined as a positive immunogenic response on at least 2 consecutive assessments post-first dose of belimumab or a single positive result at the final assessment), or
 - transient positive (defined as a single post-first dose of belimumab positive immunogenic response that does not occur at the final assessment)

Note: For the placebo cohort who proceeded to the open-label and received belimumab, the baseline result for the open-label analysis is defined as the last assessment prior to the start of belimumab treatment. The baseline result was assessed from the sample collected prior to the first dose of belimumab. The first positive post-dose assessment would be a transient positive, and if followed by a positive result in the next assessed sample, the result is considered persistent.

• Immunogenicity response (negative, persistent positive, transient positive) will be summarized by the parent randomized treatment group, and total Safety population, for each belimumab visit (including Week 16 FU and Month 6 FU visits). Note, collection of samples for immunogenicity testing at the Month 6 FU visit is reserved for subjects with a prior positive immunogenicity result such as from the Week 16 FU visit. Any Month 6 FU visit result for subjects having had a prior positive result will be summarized.

Additionally, the immunogenicity response will be summarized for any time post baseline in which a subject will be counted once only, based on the highest binding

- confirmatory assay result (lowest to highest result: Negative, Transient Positive, Persistent Positive).
- Immunogenicity response post-first dose will also be summarized by year interval in which the latest value in the year interval will be reported (usually Week 48 visit, but when not available, Week 24 or Exit visit value will be used).
- A summary of all (including baseline) immunogenicity results based on the highest binding confirmatory assay result will be produced by parent randomized treatment group, and the total Safety population. If a subject had Negative and Positive confirmatory results during the entire study period, they will be included in the Positive category.
- A quartile assessment of the titer value will not be performed due to the low number of positive results.

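### SAP 7.4.6 classifies antibody response from post-dose samples alone, so antibody present before belimumab and found again afterwards is counted as if it first appeared on the drug

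*SAP*

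**What the plan says.** SAP 7.4.6 builds its categories from the confirmatory binding result. Persistent positive is a "positive immunogenic response on at least 2 consecutive assessments post-first dose of belimumab", or one positive at the final assessment. Transient positive is "defined as a single post-first dose of belimumab positive immunogenic response that does not occur at the final assessment". Neither carries a condition on the sample taken before the first belimumab dose.

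A note on subjects who came from placebo says where their baseline comes from: "The baseline result was assessed from the sample collected prior to the first dose of belimumab". It then moves to the post-dose samples without using that result: "The first positive post-dose assessment would be a transient positive", and a second positive at the next sample makes it persistent.

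Besides the by-visit display, the SAP plans three summaries:

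- Under one, "the immunogenicity response will be summarized for any time post baseline in which a subject will be counted once only", at the highest category reached.
- One by year interval uses the latest result in each year.
- The third pools everything: "A summary of all (including baseline) immunogenicity results based on the highest binding confirmatory assay result will be produced". A subject with both negative and positive results goes into the Positive group.

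SAP 2.2 lists immunogenic response among the endpoints for the primary safety objective. Protocol 8.1.3 asks for immunogenicity to be summarised at baseline as well as during treatment and follow-up. Neither document defines treatment-emergent or treatment-boosted antibody.

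**The concern.** A reader will take a count of persistent or transient positives as the frequency with which belimumab provoked antibody. The counting rule does not isolate that. It combines subjects who turned positive on treatment with subjects who already reacted in the assay and still did so later.

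The SAP separates pre-existing from new findings elsewhere. SAP 7.2.1 counts an adverse event already ongoing before open-label belimumab, in a former placebo subject, only if it worsened. SAP 7.4.4 and 7.4.5 present laboratory results as shifts from baseline. Immunogenicity departs from this without a stated reason, and the SAP's table of changes from the protocol (SAP 2.1) does not mention it.

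At stake is attribution for a safety endpoint with few events, where moving one subject is visible.

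**Working it through.** The plan states no figure to reproduce. The check has three parts.

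**1. Is a pre-belimumab sample available?**

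- Protocol 6.3.13.1: sample before dosing at Day 0 of BEL114333. This is the baseline for former BEL113750 placebo subjects.
- SAP 11.1.2.1: sample at Week 0 of BEL113750, with a footnote requiring completion before dosing. This is the baseline for those randomised to belimumab there.
- SAP 11.1.2.2.1: samples at Day 0 and Week 52 of BEL112341. These are the baselines for its belimumab and placebo arms. The reproduced schedule has no pre-dose footnote on this row.

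So a sample is scheduled at each arm's baseline visit. Individual values may still be missing.

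**2. Does the baseline result change the classification?** Apply the SAP 7.4.6 rules literally to every pattern of three post-dose samples (P positive, N negative).

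| Post-dose pattern | Category (any baseline) | All-results summary, baseline N | All-results summary, baseline P |
|---|---|---|---|
| NNN | Negative | Negative | **Positive** |
| NNP | Persistent | Positive | Positive |
| NPN | Transient | Positive | Positive |
| NPP | Persistent | Positive | Positive |
| PNN | Transient | Positive | Positive |
| PNP | Persistent | Positive | Positive |
| PPN | Persistent | Positive | Positive |
| PPP | Persistent | Positive | Positive |

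The category column needs no baseline input: 1 negative, 2 transient and 5 persistent, whatever the subject's status before treatment. Four samples give 16 patterns: 1 negative, 3 transient, 11 persistent, and 1 (PNPN) that fits no category. That last pattern is a separate small gap. These are counts of patterns, not expected frequencies.

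Two results follow. A baseline-positive subject with any of the 7 patterns containing a post-dose positive gets the same label as a newly positive subject. A baseline-positive subject with pattern NNN is negative in the categories but Positive in the all-results summary.

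**3. How much could it matter?** Let N be the subjects assessed, k those positive after dosing, and b those among the k who were also positive at baseline. Suppose there are no other baseline positives.

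- Planned rate: k / N
- Rate of newly appearing antibody: (k − b) / (N − b)

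The documents give none of these numbers. For illustration only, assume k = 4, N from 80 to 120, and b from 0 to 2.

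| N | Planned, 4/N | b = 0 | b = 1: 3/(N − 1) | b = 2: 2/(N − 2) |
|---|---|---|---|---|
| 80 | 5.0% | 5.0% | 3.8% | 2.6% |
| 100 | 4.0% | 4.0% | 3.0% | 2.0% |
| 120 | 3.3% | 3.3% | 2.5% | 1.7% |

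The planned rate exceeds the new-onset rate by 0% when b = 0, about 32% when b = 1, and about 95% to 97% when b = 2. N hardly affects the ratio; b/k drives it, and b/k is unknown.

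**The case against.** The best reply is that the documents show no baseline-positive subject, so the problem may be empty. That stands: any figure for overstatement comes from assumed inputs, and zero belongs in the range.

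Second, baseline status is not hidden. Protocol 8.1.3 calls for a baseline summary. Table 2.81 is by belimumab visit, and Year 1 Day 0 is a named visit in SAP 11.2.2, so a baseline row is plausible. Listing 44 gives results by subject, and the table shells are in a separate document not available here. This also stands in part. But a baseline count and a post-dose count do not give the number who went from negative to positive; the reader would have to rebuild it from the listing.

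Third, the all-results summary is openly described as including baseline. It appears to be Table 2.83, judging by the title, and its programming note points to a parent-study display. It is an ever-positive table, and a separate post-baseline summary exists. That is a fair reason to keep it and not to remove the baseline result from it.

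Fourth, the study is descriptive, with no hypothesis test, and the schedule places immunogenicity under exploratory laboratory assessments. That limits the consequence. It does not settle what the reported percentage means.

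Finally, antibody present at baseline can rise on treatment, which would be a genuine response. SAP 7.4.6 describes titration for BEL114333 subjects, and neither document shows that parent-study baseline samples were titred. No titre-rise threshold is given. A boosted category cannot simply be added.

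**Conclusion.** The point holds in limited form. The rules in SAP 7.4.6 do not distinguish antibody that was present before belimumab and found again afterwards from antibody that first appeared on belimumab. The all-results summary also counts a purely pre-treatment positive as Positive. The SAP text describes no summary of new-onset incidence.

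The size cannot be computed. It depends on how many post-dose positives were also baseline-positive: none means no effect. SAP 7.4.6 cites a low number of positive results as its reason for dropping the titre quartiles, so one such subject would be a noticeable share.

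A reader might infer more than this, in three ways that the documents do not support:

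- That every baseline-positive subject is counted as a responder. The categories require at least one post-dose positive.
- That belimumab immunogenicity is overstated by a known percentage. The percentages above follow from assumed counts.
- That pre-existing antibody cannot be seen anywhere. A baseline summary and a by-subject listing are planned.

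It is worth correcting before the tables are produced, because it concerns the meaning of an endpoint under the primary objective and needs no new data.

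**What to change.** Keep the three categories and add baseline status beside them.

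- In the any-time-post-baseline and year-interval summaries, cross-tabulate the post-dose category by baseline status: negative, positive, missing.
- Report the incidence of new post-dose positivity with baseline-negative subjects as the denominator.
- Keep the all-results summary, but put subjects positive only at baseline on a separate row.
- For baseline-positive subjects, list baseline and post-dose titres where they exist. Do not label anyone boosted unless a titre-rise threshold is specified in advance.

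The cost is one derived baseline-status flag and a few extra rows. No new samples or assays are needed. With few positives, some cells will hold one subject or none, which is acceptable in a descriptive table.

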8. EFFICACY ANALYSES

The efficacy analyses will be based on the Safety population, unless otherwise specified. Further details of efficacy endpoints are provided in Appendix 5: Derived and Transformed Data.

8.1. Overview of SRI and Secondary Efficacy Endpoints

Table 12 provides an overview of the planned analyses for the SRI and secondary efficacy endpoints, with further details of data displays being presented in Appendix 12: List of Data Displays.

Table 12 Overview of Planned Efficacy Analyses

Endpoint	Sumr	Summary					
	T	F	L				
SRI Response							
SRI Response	Υ	Υ	Υ				
SELENA SLEDAI [1]							
SELENA SLEDAI ≥ 4 Point Reduction from BL	Υ	Υ	Υ				
PGA [1]							
PGA No Worsening (Increase of < 0.30 points from BL)	Υ	Υ	Υ				
BILAG [1]							
BILAG No New 1A/2B Organ Domain Scores	Υ	Υ	Υ				
Prednisone							
Number of days of daily prednisone ≤ 7.5 mg/day and/or reduced by 50% from BL	Y		Y				
SFI Flare							
Time to First Severe SFI Flare	Υ	Υ	Υ				

NOTES:

- BL = Baseline, T = Table, F = Figure, L = Listing, Y = Yes display generated, (xN) = Number of separate displays
 generated
- Summary = Represents TFL related to any summaries (i.e. descriptive statistics) of the observed raw data.
- Individual = Represents FL related to any displays of individual subject observed raw data.
- [1] Component endpoints of the composite SRI response.

8.1.1. SRI Response Rate

The proportion of subjects achieving an SRI response will be summarised by parent randomised treatment group, and the total Safety population, for each belimumab visit (every Week 24 and Week 48 visit). Total Safety population data will be displayed graphically using a line graph.

The SRI response is defined as:

- ≥ 4 point reduction from baseline in SELENA SLEDAI score, **AND**
- No worsening (increase of < 0.30 points from baseline) in Physician's Global Assessment (PGA), AND

• No new British Isles Lupus Assessment Group of SLE Clinics (BILAG) A organ domain score or 2 new BILAG B organ domain scores compared with baseline at the time of assessment.

Note: This third bullet is more clearly written as, "No new British Isles Lupus Assessment Group of SLE Clinics (BILAG) A organ domain score and at most 1 new BILAG B organ domain score compared with baseline at the time of assessment."

8.1.2. SELENA SLEDAI ≥ 4 Point Reduction from Baseline

The proportion of subjects with a reduction from baseline of ≥ 4 points in SELENA SLEDAI score will be summarised by parent randomised treatment group, and the total Safety population, for each belimumab visit (every Week 24 and Week 48 visit). Total Safety population data will be displayed graphically using a line graph.

8.1.3. PGA No Worsening

Scoring of the PGA scale ranges from 0-3, where 0 indicates no disease activity.

The proportion of subjects with no worsening in PGA (defined as an increase < 0.30 points from baseline, using the re-scaled score 0-3 scale) will be summarised by parent randomised treatment group, and the total Safety population, for each belimumab visit (every Week 24 and Week 48 visit). Total Safety population data will be displayed graphically using a line graph.

8.1.4. BILAG No New 1A/2B Organ Domain Scores

The proportion of subjects with no new BILAG A and at most 1 new BILAG B organ domain scores (No New 1A/2B) compared to baseline at the time of the assessment, will be summarised by parent randomised treatment group, and the total Safety population, for each belimumab visit (every Week 24 and Week 48 visit). Total Safety population data will be displayed graphically using a line graph.

8.1.5. Number of Days of Daily Prednisone ≤ 7.5 mg/day and/or Reduced by 50% from Baseline

The number of days of daily prednisone dose ≤ 7.5 mg/day and/or reduced by 50% from baseline will be summarised at each Week 24 and 48 belimumab visit (in every year) and at any time post-baseline. Only subjects receiving a prednisone dose ≥ 7.5 mg/day at the baseline visit will be included.

For subjects who have attended Week 24 and 48 belimumab visits (in every year), the number of days from first day of belimumab (given on the baseline visit) of daily prednisone dose ≤ 7.5 mg/day and/or reduced by 50% compared to the baseline visit will be summarised, using descriptive statistics.

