6.2.1.2. Secondary Endpoints

- Percent of subjects with ≥ 4 point reduction from baseline in SELENA SLEDAI score assessed every 24 weeks.
- Number of days of daily prednisone dose ≤ 7.5 mg/day and/or reduced by 25% from baseline over time.
- Time to first severe SLE Flare Index (SFI) flares assessed over time.

NOTE: Baseline will be defined as study Day 0 of BEL113750 study or C1115 study as appropriate. Additionally, for the group of subjects who received placebo in BEL113750, a secondary analysis will be performed by defining the baseline as Day 0 of the current study the day placebo subjects in BEL113750 will have begun to receive belimumab treatment. (See Section 8.1)

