2.4.1. Treatment Comparisons

All subjects will be treated with open-label IV belimumab for the duration of the study BEL114333. The analyses will be performed on data from all subjects as one total belimumab treatment group by year of belimumab treatment.

As subjects started to receive belimumab treatment in the parent study, or the open-label extension of the parent study BEL112341, or the open-label study BEL114333, different time points to start of belimumab treatment will be used to define subject follow up in the analysis. See Figure 1.

Analyses will be based on all available follow-up from the first dose of belimumab treatment through to study end.

Additional safety (e.g., labs), efficacy and study population summaries will be presented by parent study randomised treatment groups (belimumab vs placebo); however, these comparisons will be descriptive in nature. For the remainder of the document, parent randomised treatment group will be used to refer to the treatment to which a subject was randomised in the parent study, irrespective of formulation.

Figure 1 First Belimumab Dose/Baseline Definition

Analyses will be based on all available data from the first belimumab dose through to study end, BEL114333. As subjects started to receive belimumab in the parent study, or the open-label extension of BEL112341, or the open-label study BEL114333, different timepoints to start of belimumab treatment are used in the analysis (as shown). Baseline is defined as the last available value prior to the first belimumab dose.

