5.1. General Data Considerations

- This is a multi-centre study in Japan and Korea. There are no planned adjustments made for multiple centres or regions.
- As no formal hypotheses are being tested, there are no planned adjustments for multiple comparisons or multiplicity.
- As all subjects will be treated with belimumab and there are no hypothesis tests, no additional strata or covariates will be employed in the analyses. Subgroups will be defined for further exploration of the data in a descriptive fashion.
- Reporting of data is by year of belimumab treatment beginning on the date when subjects received their first dose of belimumab, irrespective of the formulation (Section 2.4.1 and Section 11.2.1).
- Baseline is defined as the last available value prior to the initiation of treatment with belimumab and will henceforth be referred to as 'Belimumab baseline'. See Appendix 4: Data Display Standards & Handling Conventions for more details on baseline definitions.
- For summaries performed by belimumab visit, placebo subjects are aligned based on start of exposure to belimumab (see Section 11.2.2 for details of the visit mapping).
 - Note, for BEL114333, subjects randomized to belimumab in the parent study were off-set by an additional 4 weeks compared to the open-label visit schedule, in order to complete the final assessments at the parent study Week 52 visit. Therefore, the mapping was adjusted in order to align the ensuing open-label visits. This was achieved by mapping the parent study Week 52 visit to the Belimumab Visit Year 1 Week 48 (and dropping the parent study Week 48). Ongoing open-label visits will always align.

Note, for subjects ongoing in BEL114333 at the time of study end, there is one year off-set between the parent randomised treatment groups until the last dose was administered in March 2018. Data for the last year will be limited to the belimumab group.

• There is a single data base that captures both parent study (i.e. DB phase of BEL113750) and open-label data for study BEL113750. The dividing line between parent study and open-label data is determined by the Day 365 visit. Any new data after this visit is regarded as open-label.

Note, after the database was frozen for the parent study analysis (DB data), technical limitations required the entire data base to be open in order to enter open-label information. Thus, sites had the ability to also change data pertaining to the parent study.

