11.1. Appendix 1: Time & Events

11.1.1. BEL114333 Protocol Defined Time & Events

11.1.1.1. Open-label Year 1

Study Visit	Wk 48 of BEL 113750/ On/before Day 168 of C11151	Wk 0 (Wk 52 of BEL11375 0/Day 168 of C1115) +1 week ¹	Wk 4	Wk 8	Wk 12	Wk 16	Wk 20	Wk 24	Wk 28	Wk 32	Wk 36	Wk 40	Wk 44	Wk 48	EXIT ²	16 wk FU ± 7d post infusion	6 month FU ± 7d post infusion
Study Day		Day 0	28 ±7d	56 ±7d	84 ±7d	112 ± 7d	140 ±7d	168 ±7d	196 ±7d	224 ±7d	252 ±7d	280 ±7d	308 ±7d	336 ±7d			
Written Informed Consent	Х																
Inclusion/Exclusion Criteria		X*															
Efficacy Assessments																	
Disease Activity Scales: SELENA SLEDAI, SLE Flare Index, BILAG and PGA ³		Х						x						Х	х		
SLICC/ACR Damage Index		Х												Х	Х		
Safety Assessments																	
Symptom-driven Physical Exam		X						Х						Х	Х	Х	
Record Concurrent Medications		Х	Х	Х	Х	Х	Х	Х	Χ	Х	Х	Х	Х	Х	Х	Х	
Assess/Record Adverse Events ⁴		Х	Х	Х	Х	Х	Х	Х	Χ	Х	Х	Х	Χ	Х	Х	Х	
Vital Signs 5, 11		Χ	Χ	Χ	Χ	Χ	Χ	Χ	Χ	Χ	Χ	Χ	Χ	Χ	Χ	Х	

Study Visit	Wk 48 of BEL 113750/ On/before Day 168 of C11151	Wk 0 (Wk 52 of BEL11375 0/Day 168 of C1115) +1 week ¹ Day 0	Wk 4	Wk 8	Wk 12	Wk 16	Wk 20	Wk 24	Wk 28	Wk 32	Wk 36	Wk 40	Wk 44	Wk 48	EXIT ²	16 wk FU ± 7d post infusion	6 month FU ± 7d post infusion
Study Day			±7d	±7d	±7d	$\pm 7d$	±7d										
Laboratory Assessments																	
Labs: Haematology & Modified Chem 20 (non fasting) ⁵		Х	Х		х			Х			х			Х	Х	Х	
Urinalysis ⁵		Х	Χ		Χ			Χ			Χ			Х	Х	Χ	
Spot urine (protein to creatinine ratio) ^{5, 6}		Х						Х						Х	Х		
Urine Pregnancy Test 5,7		Х	Х	Х	Х	Х	Х	Х	Х	Х	Х	Χ	Χ	Х	Х	Х	
C3, C4, Anti-ds DNA Autoantibodies ⁵		Х						Х						Х	Х		
IgG ^{5, 8}		Х			Χ			Χ						Х	Х	Х	
IgA & IgM ^{5, 8}		Х												Х	Х		
PT/ PTT		X*															
Exploratory Lab Assessments																	
Immunogenicity 9		Х						Χ						Х	Х	Χ	X ^{9A}
B cell Markers 10		Χ												Х	Х		Χ
Investigational Product																	
Belimumab Administration 11, 12		Х*	Х	Х	Χ	Х	Х	Х	Х	Х	Х	Х	Х	Х			

Calendar represents a yearly (48-week) ongoing visit schedule until the subject is terminated from the study. During the first 48 weeks, the 1st visit is Baseline/Day 0. For all subsequent 48 week calendar years, the 1st visit will be Week 4. Note: BEL112341 is referred to as 'C1115' in this time and events table.

*See footnote 1.

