11.2.2. Belimumab Visits

- For summaries performed by belimumab visit, placebo subjects are aligned based on start of exposure to belimumab.
- Baseline for both belimumab and placebo randomized subjects will be the last non-missing value prior to or on the first treatment date, except for corticosteroid use, which is the last 7 days prior to treatment start date.
- Visits will be aligned so that each visit represents equivalent exposure time to belimumab, regardless of parent study treatment, and will be mapped accordingly based on the endpoint and scheduled visits collected.

	BEL1	13750	BEL1	12341
Belimumab	Parent Randomize	d Study Treatment	Parent Randomize	d Study Treatment
Visit Name	Belimumab	Placebo	Belimumab	Placebo
		PS Week 52/		
Year 1 Day 0	PS Week 0	OL Year 1 Week 0	Day 0	Day 364/Exit
Year 1 Week 4	PS Week 4	OL Year 1 Week 4	PS Day 28	PS Day 28 OLE
Year 1 Week 8	PS Week 8	OL Year 1 Week 8	PS Day 56	
Year 1 Week 12	PS Week 12	OL Year 1 Week 12	PS Day 84	PS Day 84 OLE
Year 1 Week 16	PS Week 16	OL Year 1 Week 16	PS Day 112	
Year 1 Week 20	PS Week 20	OL Year 1 Week 20	PS Day 140	
				PS Day 168 OLE/
Year 1 Week 24	PS Week 24	OL Year 1 Week 24	PS Day 168	OL Year 1 Week 0
Year 1 Week 28	PS Week 28	OL Year 1 Week 28	PS Day 196	OL Year 1 Week 4
Year 1 Week 32	PS Week 32	OL Year 1 Week 32	PS Day 224	OL Year 1 Week 8
Year 1 Week 36	PS Week 36	OL Year 1 Week 36	PS Day 252	OL Year 1 Week 12
Year 1 Week 40	PS Week 40	OL Year 1 Week 40	PS Day 280	OL Year 1 Week 16
Year 1 Week 44	PS Week 44	OL Year 1 Week 44	PS Day 308	OL Year 1 Week 20
	PS Week 52/OL			
Year 1 Week 48	Year 1 Week 0	OL Year 1 Week 48	PS Day 364/Exit	OL Year 1 Week 24
	is not mapped to a belim			other visits and
	t is used for any derivation			OL Vanid Wask 20
Year 2 Week 4	OL Year 1 Week 4	OL Year 2 Week 4	PS Day 28 OLE	OL Year 1 Week 28
Year 2 Week 8	OL Year 1 Week 8	OL Year 2 Week 8	DO D 04 01 E	OL Year 1 Week 32
Year 2 Week 12	OL Year 1 Week 12	OL Year 2 Week 12	PS Day 84 OLE	OL Year 1 Week 36
Year 2 Week 16	OL Year 1 Week 16	OL Year 2 Week 16		OL Year 1 Week 40
Year 2 Week 20	OL Year 1 Week 20	OL Year 2 Week 20		OL Year 1 Week 44
V 0W 104	01.77	01.1/ 01/1/ 1.04	PS Day 168 OLE/	01.7/ 4.7/ 1.40
Year 2 Week 24	OL Year 1 Week 24	OL Year 2 Week 24	OL Year 1 Week 0	OL Year 1 Week 48
Year 2 Week 28	OL Year 1 Week 28	OL Year 2 Week 28	OL Year 1 Week 4	OL Year 2 Week 4
Year 2 Week 32	OL Year 1 Week 32	OL Year 2 Week 32	OL Year 1 Week 8	OL Year 2 Week 8

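### The prednisone day count in SAP 8.1.5 has no denominator, so its any-time row is confounded with belimumab follow-up that differs by design between the parent randomised groups

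*SAP*

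**What the plan says.** Protocol 6.2.1.2 lists among its three secondary efficacy endpoints: "Number of days of daily prednisone dose ≤ 7.5 mg/day and/or reduced by 25% from baseline over time". SAP 2.1 (Table 1) changes the threshold from 25% to 50% and gives its reason. The measure stays a count of days: "The number of days of daily prednisone dose ≤ 7.5 mg/day and/or reduced by 50% from baseline will be summarised" (SAP 8.1.5). The same sentence sets the time points, by visit and over the whole period: the count "will be summarised at each Week 24 and 48 belimumab visit (in every year) and at any time post-baseline". The by-visit part is limited to attendees and runs from the first dose: "For subjects who have attended Week 24 and 48 belimumab visits (in every year), the number of days from first day of belimumab". Only subjects on at least 7.5 mg/day at baseline enter. No percentage, rate or days-observed figure is specified.

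On follow-up, SAP 2.4.1 says: "Analyses will be based on all available follow-up from the first dose of belimumab treatment through to study end". SAP 5.1 acknowledges that, for subjects still in the study at its end, "there is one year off-set between the parent randomised treatment groups until the last dose was administered in March 2018". SAP 3.2 records that Korean sites closed in 2015, while the last visit in Japan was in September 2018. SAP 11.2.2 states: "Visits will be aligned so that each visit represents equivalent exposure time to belimumab, regardless of parent study treatment".

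SAP 2.1 and 2.4.1 present efficacy by parent randomised group, and SAP 11.4.1 pools IV and SC subjects within each group.

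**The concern.** A count of qualifying days is the product of two things: the share of days on which the criterion is met, and the number of days watched. Only the first is steroid sparing. Over a common window the count can be read directly. Here the window starts about a year earlier for parent-belimumab subjects and can run for several years, so the any-time row would favour that group even if steroid use were identical.

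The by-visit rows are cumulative as well, so they rise from visit to visit at constant steroid use. They also inherit a 4-week difference, because the visit map relabels parent Week 52 as Year 1 Week 48 for parent-belimumab subjects only.

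The plan handles the same problem elsewhere. Adverse events (SAP 7.2.2) and SFI flares (SAP 8.2.5) are given per 100 person-years. At stake is whether a reader of Table 3.5 can interpret a secondary endpoint that the protocol names.

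**Working it through.** **Inputs.** The double-blind phase of each parent study is 52 weeks and the SC open-label extension is 24 weeks (SAP 11.1.2). An open-label year is 48 weeks: "Calendar represents a yearly (48-week) ongoing visit schedule until the subject is terminated from the study". The last mapped visit for each source group is in the SAP 11.2.2 table.

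**Longest scheduled time from first belimumab dose, F**

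| Source group | Last mapped visit (open-label study) | Weeks | Days |
|---|---|---|---|
| IV parent, belimumab | Year 7 Week 4 | 52 + 6×48 + 4 = 344 | 2408 |
| IV parent, placebo | Year 7 Week 4 | 6×48 + 4 = 292 | 2044 |
| SC parent, belimumab | Year 4 Week 24 | 52 + 24 + 3×48 + 24 = 244 | 1708 |
| SC parent, placebo | Year 4 Week 32 | 24 + 3×48 + 32 = 200 | 1400 |

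**Check against the plan's own figure.** For the IV parent study, 344 − 292 = 52 weeks, which is the one-year off-set stated in SAP 5.1.

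**Any-time row.** If a subject qualifies on a share p of days, the count is p × F. With the same p in both groups, p cancels from the ratio:

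- IV: 2408 / 2044 = 1.18
- SC: 1708 / 1400 = 1.22

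As an illustration, at p = 0.5 (assumed) the counts are 1204 against 1022 days (IV) and 854 against 700 days (SC). SAP 11.2.1 includes follow-up visits in the any-time period. Adding 16 weeks to every group gives 360/308 = 1.17 and 260/216 = 1.20, so the result barely moves.

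**By-visit rows.** The surplus for parent-belimumab subjects is 52 − 48 = 4 weeks, or 28 days, from Year 1 Week 48 onward in both parent studies:

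- Year 1 Week 48: 364 against 336 days; 28/336 = 8.3%
- Year 2 Week 24: 532 against 504 days; 28/504 = 5.6%
- Year 6 Week 48 (IV only): (52 + 5×48)×7 = 2044 against 6×48×7 = 2016 days; 28/2016 = 1.4%

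**Does follow-up dominate the any-time count?** A simulation took the count as follow-up times p, with p independent of follow-up (assumed). The percentage of between-subject variance explained by follow-up was:

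| Follow-up scenario | Mean p = 0.5 | Mean p = 0.8 |
|---|---|---|
| All at group maxima, four groups in equal numbers | 5% to 45% (SD of p 0.41 to 0.11) | 31% to 76% (SD 0.23 to 0.09) |
| Early exits, uniform over 24 to 344 weeks | 23% to 81% | 70% to 94% |

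The answer depends on the spread of p and on actual exits. The documents give neither.

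**After the fix.** Dividing each count by F gives p in every group, so equal steroid sparing shows as a ratio of 1.00.

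**The case against.** The best case for the plan has five parts.

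1. The unequal follow-up is disclosed in SAP 5.1. Table 1.3 reports person-years by parent group, and every comparison is descriptive, so no test or error rate is affected. This is true. However, Table 1.3 covers the whole Safety population, whereas 8.1.5 is restricted to subjects on at least 7.5 mg/day at baseline. A reader cannot recover the missing denominator from it.

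2. Other steroid displays do not depend on cumulative days: average-dose change and the proportions crossing 7.5 mg/day (SAP 8.2.11 to 8.2.13), and category shifts (7.1.4). This stands. Conclusions on steroid sparing need not rest on Table 3.5, which limits the harm.

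3. Section 8.1.5 does not itself mention the group split, and the mock shells are a separate document. The split is inferred from SAP 2.1 and 2.4.1, and the shell might show days observed. This is a fair caveat. Even in a single total column, the any-time count still mixes subjects with very different follow-up.

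4. The by-visit rows are nearly aligned. This stands: the surplus is fixed at 28 days and shrinks in relative terms.

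5. The protocol defines the endpoint as a number of days. This also stands, so the count should be kept.

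A reader might also infer that the spread is 72%, from 344/200 = 1.72. That sets IV-parent belimumab against SC-parent placebo. Because SAP 2.1 and 11.4.1 pool IV and SC subjects within each parent group, no planned efficacy table for this endpoint shows that contrast.

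**Conclusion.** The any-time row of Table 3.5 is confounded with length of follow-up. It should not be compared across parent groups or read as steroid sparing without a denominator. At the scheduled maxima and equal qualifying shares, the artefact is about 18% (IV) or 22% (SC) in favour of the parent-belimumab group. The by-visit rows have the same fault on a smaller scale, from 8.3% down to about 1.4%.

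The ratios rest on scheduled maxima, not observed follow-up, and on equal qualifying shares. Actual ratios will depend on exits, on the early Korean closure and on the IV/SC mix in each pooled column; with the same mix in both columns and all subjects at their maxima, the pooled ratio lies between 1.18 and 1.22.

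A reader might go further and infer that the row largely measures follow-up instead of steroid sparing. The documents do not support that. The simulated contribution of follow-up ranges from 5% to 94% of the variance across assumptions that the documents cannot settle, and a subject who never qualifies scores zero days however long the follow-up.

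**What to change.** Keep the protocol-defined day count. In SAP 8.1.5 and Table 3.5, add two quantities for each subject: the days observed from first belimumab dose (to the visit for by-visit rows, to the last visit for the any-time row), and the percentage of those days meeting the criterion. Use the same window for numerator and denominator. State that any comparison between groups or over time is based on the percentage.

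The cost is one derived variable and extra table rows. Prednisone-equivalent dose (SAP 11.5.3), study day and date of last visit (SAP 11.5.1) are already specified, so no new data are needed. The percentage will not correct for later by-visit rows containing only subjects still attending, so the number contributing should be shown at each visit.
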